2.2.3 CD33 monoclonal antibodies in AML (GO, Mylotarg)

CD33 is a member of the sialic acid-binding immunoglobulin-like lectins (Siglecs) and is a myeloid differentiation antigen ¹⁸ primarily expressed at very early stages on myeloid progenitors. CD33 is highly (>90%) expressed on AML blasts ¹⁹. Conjugated antibodies were engineered with the intention of improving the anti-tumor efficacy of CD33 antibodies by leveraging the endocytolytic property of CD33.

Thus far the largest clinical experience with a monoclonal antibody in AML has been with GO, a humanized CD33-directed antibody drug conjugate (ADC) covalently linked to a semisynthetic derivative of a potent DNA-damaging toxin calicheamicin. In 2000, GO was granted accelerated approval by the United States FDA ²⁰ on the basis of a 30% overall response rate (CR + CRi) in phase II clinical trials ²¹ in patients with AML in first relapse ²². Response duration was difficult to determine due to the high prevalence of post-remission therapies, however, responses were relatively short.

However, no difference in OS was observed in the subsequent phase III SWOG S0106 trial designed to meet FDA post-approval requirements ²³. The lack of clear clinical benefit, concerns about increased side effects, and slightly increased early death rate with GO in this SWOG trial ²³, led to voluntary withdrawal of the drug from United States markets.

Particular concerns were related to life-threatening sinusoidal obstruction syndrome or veno-occlusive disease, which was more likely to occur when the drug was used in higher concentration, in combination with hepatotoxic agents, or within three months of allogeneic stem cell transplant (SCT) (incidence rate 9-14%) ²⁴. The postulated mechanisms included either dissociation of calicheamicin from the anti-CD33 antibody causing direct toxic effect to hepatocytes or uptake of GO by CD33(+) cells residing in the hepatic sinusoids ²⁵. The potential benefits of GO in this trial might have been masked due to a suboptimal dosing schema as well as failure to perform patient subgroup analysis.

Subsequently, large randomized trials investigated GO in addition to standard induction chemotherapy in adults with newly diagnosed AML. These studies ²⁶⁻²⁸ showed statistically improved OS when GO was added to standard induction, particularly in younger patients with intermediate and/or favorable risk cytogenetics,

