3.1 Study Design Overview (Table 1)

Table 1: Study Schema and Schedule Overview

Indication	Treatment Arm	Treatment	Dosing	Escalation/ de-escalation	Major Endpoints	Fixed N (Apply stopping rules)
Salvage AML	A	OX40 (PF-04518600) alone	D1 and D14 of a 4 wk cycle	4 patients	RP2D/MTD	Closed (as of 6/4/19) 4 treated
	B	Azacitidine + venetoclax + GO	-Aza D1-7 of a 4wk cycle -Ven D1-28 -GO D8		1. CR/CRp/PR per IWG2003	30
	C	Azacitidine + GO + avelumab	-Aza D1-7 of a 4wk cycle -GO D8 -Avelumab D1 and D14		1. CR/CRp/PR per IWG2003	24
	D	Azacitidine + venetoclax + avelumab	-Aza D1-7 of a 4wk cycle -Ven D1-28 Avelumab D1 and D14		1. CR/CRp/PR per IWG2003	24
	E	Azacitidine + avelumab + OX40	-Aza D1-7 of a 4wk cycle -Both OX40 and avelumab D1 and D14		1. CR/CRp/PR per IWG2003	Closed (as of 3/18/20) 0 treated
	F	GO + Glasdegib	Glasdegib po daily in 4 wk cycle -GO D1, D4 and D7		1. CR/CRp/PR per IWG2003	Closed (as of 3/18/20) 5 treated

3.2 Safety evaluation for Arm A (OX40 mAb alone in RR AML):

DLT is defined in section 3.4. A maximum of 4 patients will be enrolled in one dose level.

Only the 0.3 mg/kg dose of OX40 will be evaluated as this was the dose selected to move forward from the solid tumor OX40 single agent dose finding study (B0601002, ClinicalTrials.gov NCT02315066). Up to four patients will be enrolled at the dose level of 0.3mg/kg of OX40. If no more than 1 out of the 4 patients experienced a DLT, then this dose of OX40 will be established as the RP2D for AML and used in the subsequent combinations incorporating OX40 mAb.

3.3 DLT monitoring in each arm (B-F):

Each arm in the study will accrue up to 21 patients (Arms E-F) or up to 24 patients (Arms C-D) and 30 patients (Arm B) with pre-defined toxicity stopping rules to be implemented for early DLT evaluation as per following plan:

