- c) If a bone marrow remission (<5% blasts) or aplasia/hypoplasia is not confirmed on the Day 21 bone marrow, patients should continue venetoclax until day 28 and have a repeat bone marrow on Day 28 (+/- 3 days). If the Day 28 bone marrow shows >/=5% blasts proceed with cycle 2 if this is in the best interest of the patient. If the Day 28 bone marrow shows <5% blasts or aplasia/hypoplasia follow steps outlined in "a" and "b" above.

Treatment interruptions and dosing schedules other than the ones mentioned above can be considered after discussion with the PI and proper documentation of the rationale.

- The recommended starting dose of GO in this arm is 3 mg/m² on Day 8. In order to mitigate potential toxicity, the dose may be capped at 4.5 mg at the discretion of the treating physician. GO will not be administered for a longer duration or repeated beyond the Day 8 dosing. The GO solution, following reconstitution and dilution in saline, can be infused to deliver the dose over a 2-hour period on Day 8. During the infusion, only the syringe or IV bag needs to be protected from light. GO should never be administered as an IV push or bolus.

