- Standard of Care tests done on all AML patients at MDACC: To analyze for the presence of common somatic mutations, we routinely perform a 53-gene/28-gene panel with validated, next-generation platform sequencing on DNA extracted from bone marrow samples in the CLIA-certified molecular laboratory at MD Anderson Cancer Center at pre-treatment and end of study (if available) assessment for all AML patients at MDACC. Multiparametric flow-cytometry for minimal residual disease (MRD) assessment in AML by validated 15 color flow cytometry, cytogenetics, FISH and molecular markers

(if mutated at baseline) at baseline and on treatment to assess for MRD will be done routinely at MDACC Hematopathology lab as standard of care.

These data will automatically be available for all patients and will allow exploration of correlations between specific somatic mutations and/or cytogenetic aberrations and response in AML patients.

- Multi-stain immunohistochemistry and validated immune relevant multiparametric flow-cytometry on bone marrow aspirate (or slides) and peripheral blood at baseline, EOC2, EOC4, progression on all patients to: (a) identify the immunophenotype of tumor-infiltrating T-lymphocytes (TIL): CD8+, CD4+ effector, or CD4+ regulatory, (b) determine the quantitative expression of immune ligands on AML blasts, MSCs and (c) determine the quantitative expression of positive and negative co-stimulatory molecules on TILs pre- and post-therapy with the combination. For the analysis of the co-stimulatory ligands on leukemic blasts (defined as CD13+HLADR+CD33+CD38+), we have developed the “AML tumor ligand panel”: 4-1BBL, B7-1, B7-2, ICOSL, PDL-1, PDL-2, OX40L, CD40, CD27L, and CD137L. For the analysis of co-stimulatory molecules on T cells (CD4 T effector cells defined as CD3+CD4+Foxp3- cells; CD4 T regulatory cells defined as CD3+CD4+CD127-Foxp3+ cells, and CD8 T cells defined as CD3+CD8+) we have developed the “AML lymphocyte panel”: 4-1BB, CTLA-4, CD28, ICOS, PD-1, OX40, CD40L, LAG-3 and TIM-3. These studies may enable identification of prognostic and predictive markers and enable the identification of other immune checkpoints of significance for future checkpoint based therapeutic approaches in AML. These studies may be performed in the Department of Leukemia and Immunotherapy platform using validated MFC (or Cytof panels that we are currently validating) or through Pfizer commercial vendors depending on the more financially viable option.

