- RNA sequencing (Illumina Hi-seq) and Nanostring analysis for IO-gene signature and gene expression for “stemness” associated genes [Ng et al, A 17-gene stemness score for rapid determination of risk in acute leukaemia. *Nature*. 2016 Dec 15;540(7633):433-437.] on bone marrow aspirate (and possibly on peripheral blood) at baseline, EOC2, EOC4, and at progression
 - TCR analysis on bone marrow aspirate and peripheral blood at baseline, EOC2, EOC4, and progression on all patients
 - Serum cytokine profiling by ELISA panels at baseline, EOC2, EOC4, and progression on bone marrow aspirate and peripheral blood on all patients.

Peripheral blood up to 40 mL (within 24 hours) will be collected in patients who consent to the correlative studies for testing of biomarkers at the following time points:

-Baseline (prior to day 1 dose of drug), and on day 28 (+/- 4) on cycle 1 (done at MD Anderson), at day 28 (+/- 4 days) of cycles 2, 4, 8.

Bone marrow samples will be collected in patients who consent to the correlative studies for testing of biomarkers at baseline, on day 28, at day 28 (+/- 4 days) of cycles 2, 4, 8, and at progression (if possible).

All correlative samples are optional.

Missed samples for correlative studies will not constitute protocol deviations.

- For patients that remain on study with no significant toxicity for more than 6 months, subsequent evaluations during study may be modified after discussion with the principal investigator. These include a decrease in frequency of bone marrow aspirations to every 6-12 months (or as clinically indicated), correlative studies to every 6-12 months (or suspension of sample collection for correlative studies), other laboratory tests to once every cycle.

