8. Changes in drug dose and/or schedule must be discussed with and approved by the MDACC physician investigator, or they're representative prior to initiation, and will be documented in the patient record.

7.2.14 Patients with an objective response at completion of active study treatment will be followed for survival at MD Anderson Cancer Center (MDACC) every 3 to 6 months for up to 5 years after completion of active treatment and while still on study. If the patient is unable to return to MDACC the follow-up visits may be conducted via telephone.

Table 13. The study assessment schema is shown in tabular form below

Study Period/Cycle	Screening*	Treatment																		End of Study (EOS) ^{h,i}	Long-Term Follow-Up
		Cycle 1							Cycle 2							Cycle 3					
Cycle Day		1	8	14	15	22	28	1	8	14	15	22	28	1	8	14	15	22	1	30 Days After Last Dose	Every 3-6 months
Study Day	-14 to 0	1	8		15	22		29	36		43	50		57	64	70	71	78	—		
Complete history	X	X						X						X					X		
Physical examination ^a	X	X						X						X					X	X	
Vital Signs ^{**}		X		X				X		X				X		X			X		
Performance status	X	X						X						X					X	X	
Document all measurable disease (if present)	X																				
Concomitant medications ^a	X	X						X						X					X		X
Chest X-ray PA/Lateral	X																				
Nasal Wash PCR	X																				
ECHO/MUGA	X																		Q 3 cycles		
ECG ^k	X	X						X						X					X		
TropI, CK, CK-MB, BNP ^k	X							X						X					X		
CBC with differential ^b	X	X	X	X	X	X	X	X	X	X	X	X	X	X	X	X	X	X	X	X	

Sodium, Potassium, Chloride, glucose, uric acid, bicarbonate, BUN, Creatinine, total bilirubin, direct bilirubin, calcium, magnesium, ALT, or AST, alk phos ^b	X	X	X			X	X		X	X		X	X		X	X		X
Urinalysis	X	X						X				X				X		
Testosterone (males), GnRH	X																	
TSH, total T3, free T4, cortisol ^c	X	X						X				X				X		
Pregnancy test ^d	X																	
Bone marrow aspirate/biopsy ^e	X						X									X		
Correlative	Screening	Cycle 1					Cycle 2				Cycle 3				Subsequent cycles			EOS
Optional correlatives on blood ^f	X				Day 28				Day 28						Day 28 of cycles 2,4, 8, prog		If possible	
Optional correlatives on bone marrow ^g	X				Day 28				Day 28						Day 1 of cycle 2, 4, 8, prog		If possible	

* Samples collected at screening do not need to be repeated on Day 1 of Cycle 1.

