Demographic/clinical characteristics and safety data will be summarized using descriptive statistics such as mean, standard deviation, median and range. The composite complete response (CRc) rates, partial response (PR), hematologic improvement (HI) rate, 4-week and 8-week mortality will be estimated along with the

95% credible intervals. Kaplan-Meier method will be used to estimate the relapse-free survival (RFS), morphologic leukemia free survival (MLFS), time to next therapy (TNT) and overall survival (OS). The two-sided log-rank tests will be used to assess the differences of time to events between groups. Cox proportional hazards regression model will be used to determine associations between MRD and OS.

All patients who received at least one dose of study drug will be included in the intent-to-treat analysis for efficacy and safety. We will follow standard reporting guidelines for adverse events. Safety data will be summarized by category, severity and frequency. Paired t-tests will be used to determine the immunological and molecular changes in the peripheral blood and bone marrow from baseline to the predefined time-points on-therapy.

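### In Arms B and C the blast ligand panel gates on CD33, the target of the study drug GO; the research marrow days conflict, and the paired t-tests have no multiplicity control

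*Combined protocol and SAP*

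**What the plan says.** The correlative studies in Section 7.2.13 are optional and serve the exploratory objectives of Section 1.3.

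- **Blast gate.** Section 7.2.13 gives one definition for every arm: "For the analysis of the co-stimulatory ligands on leukemic blasts (defined as CD13+HLADR+CD33+CD38", each marker positive. It offers no alternative for arms that give GO. The three T-cell subsets are defined by CD3, CD4, CD8, CD127 and Foxp3.
- **GO.** Section 2.2.3 describes "GO, a humanized CD33-directed antibody drug conjugate (ADC" and explains that such conjugates were built by "leveraging the endocytolytic property of CD33". Table 1 lists Arm B as "Azacitidine + venetoclax + GO"; Arm C also contains GO, and Arm D does not. For both GO arms Section 5.2 states that "GO will not be administered for a longer duration or repeated beyond the Day 8 dosing".
- **Marrow days.** The collection list in Section 7.2.13 takes research marrow "at day 28 (+/- 4 days) of cycles 2, 4, 8, and at progression (if possible". Table 13, under subsequent cycles, says "Day 1 of cycle 2, 4, 8, prog". Footnote g keeps day 28 but names only cycles 4 and 8 after the first day-28 sample. The assay list in Section 7.2.13 names end of cycle 2 (EOC2), end of cycle 4 (EOC4) and progression.
- **Test.** Section 11.0 states: "Paired t-tests will be used to determine the immunological and molecular changes in the peripheral blood and bone marrow". It gives no significance level, family of tests or adjustment.

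**The concern.** A before-and-after comparison should measure the same cell population at both times. If treatment changes which cells meet the gate, mean ligand expression inside the gate can move although no cell has changed its expression. Gating on the target of a drug that enters cells through that target, and lyses them, is the setting in which this can happen. It is most plausible at progression, when the blasts present are those that outlasted treatment.

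The conflicting marrow days mean that staff who follow the table and staff who follow the text could sample at opposite ends of a cycle. A long list of tests at an unstated level with no adjustment will also yield nominal findings by chance.

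The immune work has no bearing on treatment decisions in the trial. However, Section 2.4 presents it as valuable in its own right, and Section 7.2.13 hopes that it may point to prognostic or predictive markers and to further checkpoints to target.

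**Working it through.** The plan states no number of tests and no significance level, so there is no figure to reproduce. The counts below come from its own lists.

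**1. Reach of the CD33 gate**

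- Section 7.2.13 lists 10 molecules on blasts, and 9 molecules on each of 3 T-cell subsets: 10 + 9 × 3 = 37 readouts.
- The gate touches the 10 blast readouts in the two open GO arms: 10 × 2 = 20 of 37 × 3 = 111 readout-by-arm combinations, or 18%. The other 27 readouts, and all of Arm D, do not depend on it.
- Illustration, on assumed values: let a share f = 0.90 of blasts be CD33-positive at baseline, and let GO remove a fraction k of these and none of the rest. The gate then holds f(1 − k) / [f(1 − k) + 1 − f] of the remaining blasts. For k = 0.5 this is 0.45 / 0.55 = 82%; for k = 0.9 it is 0.09 / 0.19 = 47%.
- This shows a shift in composition, not a bias in a ligand. Bias also needs ligand expression to differ with CD33 level, on which the documents give no data. Its size and direction cannot be calculated.

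**2. Marrow days**

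| Source | Marrow after baseline |
|---|---|
| Section 7.2.13, assay list | EOC2, EOC4, progression |
| Section 7.2.13, collection list | Day 28, then day 28 of cycles 2, 4, 8, progression |
| Table 13, cycle 1 and 2 entries | Day 28 |
| Table 13, subsequent cycles | Day 1 of cycles 2, 4, 8, progression |
| Table 13, footnote g | Day 28, then day 28 of cycles 4, 8, progression |
| Section 7.2.10, clinical marrow | Day 28, then day 28 of cycles 2, 4, 8, progression |

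With 28-day cycles, Day 1 of cycle c is study day 28(c − 1) + 1, and day 28 is study day 28c:

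- cycle 2: 29 against 56
- cycle 4: 85 against 112
- cycle 8: 197 against 224

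Each gap is 27 days, against a window of ± 4 days. Study day 29 falls inside the window of the first clinical marrow (day 28 ± 4, so days 24 to 32), so the cycle 2 entry still lands on a clinical marrow. Study days 85 and 197 do not: the clinical marrows nearest to day 85 are on days 56 and 112, and those nearest to day 197 are on days 112 and 224.

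**3. Number of tests**

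Assume that every readout is tested in blood and in marrow, with arms pooled, at two-sided 5%.

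- EOC2 and EOC4: 37 × 2 × 2 = 148 tests; 148 × 0.05 = 7.4 false positives expected if nothing changes.
- Adding progression: 37 × 2 × 3 = 222 tests; 222 × 0.05 = 11.1.
- If 4-1BBL and CD137L are the same ligand, as one title in the reference list suggests, there are 36 readouts and 144 to 216 tests.
- Separate testing in the three open arms would give 444 to 666 tests, with 22.2 to 33.3 expected false positives.

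Correlation between markers does not change the expected count. It lowers the chance of at least one false positive: in a simulation of 222 tests on 24 pairs, from above 0.999 under independence to about 0.99 at correlation 0.3 and 0.81 at 0.6. Cytokine, T-cell receptor and gene expression readouts are not counted.

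**The case against.** The case against acting is substantial, and much of it stands.

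- **A reader might infer that the immune analysis as a whole compares different cells.** It does not. Only the blast ligand flow panel in Arms B and C is conditioned on CD33. Section 7.2.13 also plans multi-stain immunohistochemistry and allows mass cytometry panels, so this flow gate is not the only possible view of the blasts.
- **A reader might take CD33 loss after GO as established.** The documents report none. If the Day 8 wording means a single dose, EOC2 and EOC4 fall 56 − 8 = 48 and 112 − 8 = 104 days later, and the effect on the gate may have faded. The inference from mechanism remains, and progression is the time at which it is strongest.
- **A reader might conclude that blood and marrow are tested against each other a cycle apart.** No such test is planned; Section 11.0 tests change from baseline.
- **A reader might object to t-tests because some percentages lie near zero.** The 0.6% for OX40-positive CD8 cells in Section 2.6.1 is from healthy donors. The figures for relapsed AML are 2.3% and 2.1%, and those for PD1-positive CD8 cells are 25.5% and 34.7%. At up to 24 to 30 pairs per arm, preferring a signed-rank test or a mixed model is largely taste.
- **A reader might count 37 × 2 × 5 × 3 = 1,110 tests.** That needs testing by arm at five times, whereas the assay list has three times and nothing says that testing is by arm.
- **The marrow conflict looks like a slip in one table cell.** Probably so, but a schedule table may be what sites follow, and the omission in footnote g is a second discrepancy.

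Section 11.0 is silent on adjustment; it does not rule it out.

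**Conclusion.** The concern holds in limited form. In Arms B and C, a before-and-after change in blast ligand expression on the flow panel may partly reflect which blasts remain in the gate. This covers 10 of 37 readouts in two of three open arms, and its size is unknown. It rests on the mechanism of GO that the protocol describes, not on reported CD33 loss.

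The research marrow schedule contradicts itself by 27 days, which matters in cycles 4 and 8.

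The paired tests have no multiplicity control. The figure of about 7 to 11 expected false positives assumes a 5% level, no true change, pooled arms and every readout tested in both tissues on the assay list's schedule.

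The importance is modest. The work is exploratory and the samples are optional. The composite complete response rate, the dose-limiting toxicity evaluation and the stopping rules are untouched.

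**What to change.** 1. **Gate.** In Arms B and C, add a blast gate that does not use CD33. Apply it identically at baseline and on treatment to the same flow files, report it beside the CD33-positive gate, and report CD33 expression as a readout. No new samples are needed. The cost is a less specific gate: removing CD33 leaves CD13, HLA-DR and CD38, and the documents do not show further blast markers in this panel. For that reason both gates should be reported.
2. **Marrow days.** Correct the Table 13 marrow entry and footnote g to day 28 of cycles 2, 4 and 8, and reconcile them with the EOC2, EOC4 and progression assay list in Section 7.2.13, so that it is clear which collected samples are assayed. This is a text correction.
3. **Tests.** In Section 11.0, name the family of paired tests and apply Benjamini-Hochberg false discovery rate control within it, or label the results descriptive. The cost is fewer nominally significant markers. As an outer limit, Bonferroni correction over 222 tests with 24 pairs would raise the smallest change detectable with 80% power from 0.60 to 1.09 standard deviations; Benjamini-Hochberg at the same level is never stricter than that.
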